8.3. Adverse Events, Serious Adverse Events, and Product Complaints

The definitions of the following events can be found in Appendix 3 (Section 10.3):

- Adverse events (AEs)
- Serious adverse events (SAEs)
- Product complaints (PCs)

These events will be reported by the participant (or, when appropriate, by a caregiver, surrogate, or the participant's legally authorized representative).

The investigator and any qualified designees are responsible for detecting, documenting, and recording events that meet these definitions and remain responsible for following up events that are serious, considered related to the study drug or study procedures, or that caused the participant to discontinue the study drug or study (see Section 7).

Care will be taken not to introduce bias when detecting events. Open-ended and non-leading verbal questioning of the participant is the preferred method to inquire about event occurrences.

After the initial report, the investigator is required to proactively follow each participant at subsequent visits/contacts. All SAEs will be followed until resolution, stabilization, the event is otherwise explained, or the participant is lost to follow-up (as defined in Section 7.3).

For product complaints, the investigator is responsible for ensuring that follow-up includes any supplemental investigations as indicated to elucidate the nature and/or causality. Further information on follow-up procedures is provided in Appendix 3 (Section 10.3).

Suspected Unexpected Serious Adverse Reactions

Suspected unexpected serious adverse reactions (SUSARs) are serious events that are not listed in the IB and that the investigator identifies as related to study drug or procedure. United States 21 CFR 312.32, European Union Clinical Trial Directive 2001/20/EC, and the associated detailed guidance or national regulatory requirements in participating countries require the reporting of SUSARs. The sponsor has procedures that will be followed for the identification, recording, and expedited reporting of SUSARs that are consistent with global regulations and the associated detailed guidance.

8.3.1. Timing and Mechanism for Collecting Events

This table describes the timing, deadlines, and mechanism for collecting events.

Event	Collection Start	Collection Stop	Timing for Reporting to Sponsor or Designee	Mechanism for Reporting	Back-up Method of Reporting
Adverse Ever	nt				
AE	Signing of the informed consent form (ICF)	Participation in study has ended	As soon as possible upon site awareness	AE eCRF	N/A
Serious Adve	erse Event				
SAE and SAE updates – prior to start of study drug and deemed reasonably possibly related with study procedures	Signing of the informed consent form (ICF)	Start of study drug	Within 24 hours of awareness	SAE eCRF	SAE paper form

Event	Collection Start	Collection Stop	Timing for Reporting to Sponsor or Designee	Mechanism for Reporting	Back-up Method of Reporting
SAE* and SAE updates – after start of study drug	Start of study drug	Participation in study has ended	Within 24 hours of awareness	SAE eCRF	SAE paper form
SAE* – after participant's study participation has ended and the investigator becomes aware	After participant's study participation has ended	N/A	Promptly	SAE paper form	N/A
Pregnancy					
Pregnancy in female participants and female partners of male participants	After the start of study drug	Four months after the last injection for female partners of male participants and 2 months after the last injection for female participants	Within 24 hours of learning of the pregnancy	Pregnancy paper form eCRF	Pregnancy paper form
Product Com	plaints				
PC associated with an SAE or might have led to an SAE	Start of study drug	End of study drug	Within 24 hours of awareness	Product Complaint form	N/A
PC not associated with an SAE	Start of study drug	End of study drug	Within 1 business day of awareness	Product Complaint form	N/A

Event	Collection Start	Collection Stop	Timing for Reporting to Sponsor or Designee	Mechanism for Reporting	Back-up Method of Reporting
Updated PC information	_	_	As soon as possible upon site awareness	Originally completed Product Complaint form with all changes signed and dated by the investigator	N/A
PC (if investigator becomes aware)	Participation in study has ended	N/A	Promptly	Product Complaint form	N/A

Abbreviations: eCRF = electronic case report form; N/A = not applicable; PC = product complaint; SAE = serious adverse event.

8.3.2. Primary, Secondary, and Additional Study Endpoint Reporting

The following investigator-reported events are considered potential endpoints and must be reported first as an AE on the AE eCRF (with the appropriate designation for seriousness). They must then be reported as an endpoint on the eCRF with all required source documents provided for adjudication to the CEC. These potential endpoints (even if they meet criteria for a serious event) are not to be reported on the SAE eCRF unless considered as possibly related to study drug, the drug delivery system, or study procedure. Potential endpoints that are serious and considered as possibly related to study drug, the drug delivery system, or study procedure must also be reported as an SAE using the SAE eCRF:

- all-cause mortality (death), and
- HF events.

In the case where 1 of the above endpoint events is reported but does not meet a prespecified event definition detailed in the CEC charter, as reviewed by the independent CEC, no further action will be taken by the study site.

^{*}Serious adverse events, including death, caused by disease progression as described in Section 8.3.2 should not be reported unless the investigator deems them to be possibly related to study drug.

8.3.3. Adverse Events of Special Interest

The following are AESI and will be adjudicated by an external adjudication committee. This committee will be blinded to treatment assignment.

- pancreatitis
- major adverse CV events (see Section 10.5.1.5), and
- deaths

The following are additional AESI for this program that will not be adjudicated by an external committee:

- hepatobiliary disorders
- severe hypoglycemia
- thyroid malignancies and C-cell hyperplasia
- supraventricular arrhythmias and cardiac conduction disorders
- allergic/hypersensitivity reactions, including injection site reactions and ADA formation
- severe GI AEs, and
- acute renal events.

Sites should collect additional details and data regarding AESI, as instructed on the applicable eCRFs, and detailed in Section 10.5.

The details on the definition of AESI will be provided in SAP.

8.4. Treatment of Overdose

Considering the mechanism of action of tirzepatide, potential overdose effects can be GI disorders and hypoglycemia. In the event of overdose, appropriate supportive treatment should be initiated according to the participant's clinical signs and symptoms.

Study drug overdose (defined as injection of study drug more than 1 time within 72 hours) will be reported as an AE.

In the event of an overdose, the investigator should

- contact the medical monitor immediately
- evaluate the participant to determine, in consultation with the medical monitor, whether study intervention should be interrupted or whether the dose should be reduced, and
- closely monitor the participant for any AE/SAE and laboratory abnormalities as medically appropriate.

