10.3.1. Definition of AE

AE Definition

- An AE is any untoward medical occurrence in a participant administered a pharmaceutical product and which does not necessarily have a causal relationship with the study drug. An AE can therefore be any unfavorable and unintended sign (including an abnormal laboratory finding), symptom, or disease (new or exacerbated) temporally associated with the use of a medicinal (investigational) product, whether or not related to the medicinal (investigational) product.
- An AE is any untoward medical occurrence, unintended disease or injury, or untoward clinical signs (including abnormal laboratory finding) in study participants, users, or other persons, whether or not related to the investigational medical device. This definition includes events related to the investigational medical device or comparator and events related to the procedures involved except for events in users or other persons, which only include events related to investigational devices.

Events Meeting the AE Definition

- Any abnormal laboratory test results (hematology, clinical chemistry, or urinalysis) or other safety assessments (for example, ECG, radiological scans, vital signs measurements), including those that worsen from baseline, considered clinically significant in the medical and scientific judgment of the investigator (that is, not related to progression of underlying disease).
- Exacerbation of a chronic or intermittent preexisting condition including either an increase in frequency and/or intensity of the condition.
- New conditions detected or diagnosed after study drug administration even though they may have been present before the start of the study.
- Signs, symptoms, or the clinical sequelae of a suspected drug-drug interaction.
- Signs, symptoms, or the clinical sequelae of a suspected overdose of either study drug or a concomitant medication. Overdose per se will not be reported as an AE/SAE unless it is an intentional overdose taken with possible suicidal/self-harming intent. Such an overdose should be reported regardless of sequelae.
- "Lack of efficacy" or "failure of expected pharmacological action" per se will not be reported as an AE or SAE. Such instances will be captured in the efficacy assessments.

However, the signs, symptoms, and/or clinical sequelae resulting from lack of efficacy will be reported as an AE or SAE if they fulfill the definition of an AE or SAE.

Events NOT Meeting the AE Definition

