3.14.1. Analysis of Adverse Events

3.14.1.1. Treatment-Emergent Adverse Events

A treatment-emergent AE (TEAE) is defined as an event that first occurred or worsened in severity after the first dose of study treatment. The MedDRA lowest level term (LLT) will be used in the treatment-emergent derivation. The maximum severity for each LLT during the baseline period, including ongoing medical history, will be used as baseline severity. For events with a missing severity during the baseline period, the event will be treated as mild in severity for determining treatment-emergence. Events with a missing severity during the postbaseline period will be treated as severe and treatment-emergence will be determined by comparing to baseline severity.

For events occurring on the day of taking study medication for the first time, the case report form (CRF)-collected information (for example, treatment emergent flag, start time of study treatment, and event) will be used to determine whether the event was pre- versus posttreatment if available. If the relevant information is not available, then the events will be counted as posttreatment.

Unless otherwise specified, the counts and percentages of participants with TEAEs will be summarized by treatment using the MedDRA PT nested within SOC. Statistical comparisons will be applied at both the SOC and PT levels. Events will be ordered by decreasing frequency in tirzepatide arm within SOC. The SOC will be in alphabetical order. For events that are sexspecific, the denominator and computation of the percentage will include only participants from the given sex.

An overview of the number and percentage of participants who experienced a TEAE, serious AE (SAE), death, or discontinued from study treatment or study due to an AE will be summarized by treatment.

The counts and percentages of patients with TEAEs by maximum severity will be summarized by treatment using MedDRA PT within SOC. For each participant and TEAE, the maximum severity for the MedDRA PT is the maximum postbaseline severity observed from all associated LLTs mapping to the MedDRA PT. The maximum severity will be determined based on the nonmissing severities. If all severities are missing for the defined postbaseline period of interest, it will show as missing in the table.

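### Protocol Sections 8.4 and 10.3.1 give conflicting instructions on whether a study drug overdose without self-harm intent is recorded as an adverse event

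*Protocol*

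**What the plan says.** Protocol Section 8.4 (Treatment of Overdose) defines overdose by the interval between injections and makes it reportable: "Study drug overdose (defined as injection of study drug more than 1 time within 72 hours) will be reported as an AE". It then tells the investigator to involve the medical monitor, assess the participant and watch for adverse events and laboratory abnormalities.

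Protocol Section 10.3.1 (Definition of AE, in Appendix 3) lists, among events that meet the AE definition: "Signs, symptoms, or the clinical sequelae of a suspected overdose of either study drug or a concomitant medication". The same bullet continues: "Overdose per se will not be reported as an AE/SAE unless it is an intentional overdose taken with possible suicidal/self-harming intent". For the self-harm case it adds: "Such an overdose should be reported regardless of sequelae".

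Protocol Section 8.3 sends sites to Appendix 3 for the definitions of AE and serious AE, and makes investigators responsible for recording events that meet them. Section 8.3.1 names the AE eCRF as the reporting route for AEs.

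SAP Section 3.14.1.1 sets out how these records are used: "Unless otherwise specified, the counts and percentages of participants with TEAEs will be summarized by treatment using the MedDRA PT nested within SOC". The SAP has no separate rule for overdose.

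**The concern.** A site that learns of a second injection within 72 hours has two places to look. Section 8.4 says to record it as an AE. Section 8.3 leads to Appendix 3, which says that an overdose as such is not recorded unless self-harm intent is possible. Two sites that each follow the protocol in good faith could handle the same event in opposite ways.

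An overdose term in the treatment-emergent AE tables would then reflect which section a site consulted as well as how often overdoses happened. This matters somewhat more than usual because the product is injected weekly, normally by the participant at home, so an occasional repeat injection is foreseeable.

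**Working it through.** The plan has no figure to reproduce, and the point does not depend on alpha, power or sample size. The check is a comparison of the two rules.

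**Do the rules cover the same event?** Section 8.4 concerns study drug. The Section 10.3.1 bullet names study drug as well as concomitant medication, so it cannot be read as applying to other drugs only. They overlap on any study drug overdose that meets the 72-hour definition.

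**Does either rule yield to the other?** Section 10.3.1 names one exception, self-harm intent, and does not mention the Section 8.4 definition. Section 8.4 does not refer to Appendix 3 on overdose. No statement of precedence was found.

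**Where do they disagree?** For an overdose that meets the Section 8.4 definition:

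| Case | Section 8.4 | Section 10.3.1 | Result |
|---|---|---|---|
| No self-harm intent, no symptoms | Overdose is an AE | Overdose is not an AE | Full conflict |
| No self-harm intent, with symptoms | Overdose is an AE | Symptoms are AEs; overdose itself is not | Conflict on the overdose term only |
| Possible self-harm intent, with or without symptoms | Overdose is an AE | Overdose is reported | No conflict |

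The first two rows include accidental repeat injections and also deliberate ones made for another reason, such as catching up on a missed dose. The Section 10.3.1 exception is limited to possible suicidal or self-harming intent.

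**What reaches the analysis?** An overdose entered on the AE eCRF after the first dose is coded and counted by preferred term under SAP Section 3.14.1.1. One that is not entered is absent from those tables. With the planned 350 participants per group, each participant whose overdose is or is not entered moves that preferred term by 1/350 = 0.29 percentage points in the group. In the first row of the table, if the participant has no other AE, the count of participants with any treatment-emergent AE also changes by one. The documents do not say how many overdoses to expect, so the total effect cannot be calculated.

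**The case against.** The strongest reply is that Section 8.4 is the specific, trial-level rule and should prevail. It concerns study drug alone and gives a working definition, whereas the Appendix 3 bullet is generic and has no threshold. The amendment summary also shows that the Section 8.4 definition and the required investigator actions were revised in this amendment, and it lists no overdose change to Section 10.3.1. A site could reasonably take Section 8.4 as the updated instruction. That reading is available, but the protocol does not state it, and Section 8.3 points sites to Appendix 3 for what counts as an AE. The reply shows how the conflict may have arisen and does not remove it.

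A second reply is that little is lost, and most of this stands. The diary records the date and time of each dose (Section 6.1). The investigator reviews dosing data at study visits, and unused drug or empty cartons are returned for accountability (Section 6.4). The Section 8.4 duties to involve the medical monitor and observe the participant apply however the event is classified. Clinical consequences are AEs under either section. Overdose is not among the AEs of special interest in Section 8.3.3 and has no analysis of its own in the SAP. The trial is double-blind, so a site's choice of section should not depend on treatment group.

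A reader might infer that overdoses would go undetected and that safety surveillance is weakened. These provisions do not support that. What may vary is whether an overdose term appears on the AE eCRF.

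**Conclusion.** The protocol is wrong as written: it contains an internal inconsistency in AE reporting, minor in reach. It applies to study drug overdoses without self-harm intent, completely when there are no symptoms and for the overdose term alone when there are. The consequence is limited to the comparability across sites of overdose terms in the treatment-emergent AE tabulations. Efficacy analyses, alpha allocation and sample size are not affected.

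Two stronger readings should be avoided. A reader might infer that every asymptomatic overdose is caught in the conflict; it is not, because one with possible self-harm intent is reportable under both sections even without sequelae. A reader might also infer that sites will report differently; the documents show only that they may, since site training or data-entry guidance outside these documents could already have settled the practice.

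The conclusion rests on the current wording of Sections 8.4 and 10.3.1 and on the absence of a precedence statement in either document. It implies no view on which rule is correct.

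**What to change.** Reconcile Sections 8.4 and 10.3.1 so that a single rule states which study drug overdoses go on the AE form, and add a cross-reference in each section to the other. Tell sites how to handle overdoses already recorded or omitted, so that the final data follow one rule throughout.

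The cost is a protocol clarification letter, or wording in the next amendment, and one query to sites. Sample size, visit schedule and planned analyses do not change.

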8.5. Pharmacokinetics

Pharmacokinetic samples will be collected from all participants in this study.

Tirzepatide plasma concentrations will be determined from blood samples obtained from participants receiving tirzepatide treatment. Blood samples collected from participants assigned to the placebo arm will not be included in the bioanalysis of drug concentrations.

Blood samples for PK assessment will be collected prior to the dose administration and at the same time as the planned immunogenicity samples (that is, at Week 0 and then at Weeks 4, 12, 24, and 52 per the Study Schedule or additionally at follow-up and ET (reference SoA).

Samples will be analyzed at a laboratory approved by the sponsor and stored at a facility designated by the sponsor.

Concentrations of tirzepatide will be assayed using a validated liquid chromatography mass spectrometry method. Bioanalytical samples collected to measure tirzepatide concentrations will be retained for a maximum of 1 year following last participant visit for the study (Section 10.1.10). During this time, samples remaining after the bioanalyses may be used for exploratory analyses such as metabolism work, protein binding, and/or bioanalytical method cross-validation.

8.6. Pharmacodynamics

Pharmacodynamic parameters will not be evaluated in this study.

8.7. Genetics

A whole blood sample will be collected for pharmacogenetic analysis where local regulations allow.

See Appendix 2, Clinical Laboratory Tests (Section 10.2), and Section 1.3 (SoA) for sample collection information.

See Section 10.6 for genetic research, custody, and sample retention information.

8.8. Biomarkers

Biomarker research is performed to address questions of relevance to drug disposition, target engagement, pharmacodynamics, mechanism of action, variability of participant response (including safety), and clinical outcome. Sample collection is incorporated into clinical studies to enable examination of these questions through measurement of biomolecules including DNA, RNA, proteins, lipids, and other cellular elements.

Serum and plasma for exploratory biomarker research will be collected at the time specified in the SoA (Section 1.3) where local regulations allow.

All samples will be coded with the participant number. These samples and any data generated can be linked back to the participant only by the investigator site personnel.

Samples will be stored and analysis may be performed on biomarkers thought to play a role in disease processes, mechanism of action of tirzepatide, pathways associated with HFpEF, and/or research methods validating diagnostic tools or assay(s) related to HFpEF and associated diseases. Biomarkers may be evaluated to determine their association with observed clinical responses to tirzepatide and the disease state.

Samples will be retained at a facility selected by the sponsor or its designee for the duration detailed in Section 10.1.10, or for a shorter period if local regulations and ERBs impose shorter time limits. This retention period enables use of new technologies, response to regulatory questions, and investigation of variable response that may not be observed until later in the development of tirzepatide or after tirzepatide becomes commercially available.

8.9. Immunogenicity Assessments

At the visits and times specified in the SoA (Section 1.3), venous blood samples will be collected to determine antibody production against tirzepatide. Antibodies may be further characterized for cross-reactive binding to endogenous counterparts (native GIP and GLP-1) and their ability to neutralize the activity of tirzepatide and endogenous counterparts. To interpret the results of immunogenicity, a venous blood sample will be collected at the same time points to determine the plasma concentrations of tirzepatide. All samples for immunogenicity should be taken predose when applicable and possible.

Samples will be retained for a maximum of 15 years after the last participant visit, or for a shorter period if local regulations and ERBs allow, at a facility selected by the sponsor. The duration allows the sponsor to respond to future regulatory requests related to tirzepatide. Any samples remaining after 15 years will be destroyed.

8.10. Medical Resource Utilization and Health Economics

Not applicable.

9. Statistical Considerations

